#### Background

The global burden of pediatric mortality in low- and middle-income countries (LMICs) remains high, with 4.9 million deaths in children under 5 in 2016 [1]. Most of these deaths are due to sepsis, which is defined as the body's response to an infection (such as pneumonia, diarrhea, or malaria) leading to organ damage and ultimately morbidity and mortality [2]. Sepsis is common worldwide, but countries in Africa report substantially higher case fatality rates (adjusted odds ratios: Africa, 7.89 [95% confidence interval (CI), 6.02–10.32]) as compared to the United States [3]. Recognizing the enormity of the global burden of sepsis (death, disability, social, and economic) led to a 2017 World Health Assembly resolution highlighting the need to prioritize prevention, recognition, and early treatment of sepsis [4].

Sepsis disproportionately affects socioeconomically disadvantaged populations in LMICs. Encouragingly, most deaths from sepsis are preventable by early detection and treatment. The majority of deaths occurring in health facilities happen occur as a result of delayed, inadequate, or inappropriate treatment. Every hour of delay in therapy is associated with an escalating risk of morbidity and mortality [5]. Simple, highly effective interventions to treat sepsis, including antimicrobials and intravenous (IV) fluids, are available at care facilities in LMICs. Yet availability and readiness to provide treatment is not always enough [6] timely treatment may not occur because the sickest children are not prioritized.

The World Health Organization (WHO) advocates the use of Emergency Triage Assessment and Treatment (ETAT) guidelines to triage children in resource limited settings [7]. Although the ETAT system is widely adopted in LMICs, successful implementation of the guidelines into clinical practice is not always the case [8]. In LMICs, patients are frequently admitted and treated on a first-come, first-serve basis, leading to delayed care for children who are in need of urgent treatment. These priority children can receive faster treatment if every child is rapidly triaged upon arrival to identify danger and priority signs of sepsis [9]. However, sepsis is a syndrome that mimics many conditions and few health workers can confidently triage and diagnose sepsis. Evidence-based trigger tools and protocols may be useful in skilled hands, but require complex decisionmaking based on physiological, clinical, social, and laboratory parameters.

The purpose of this study is to develop and clinically evaluate a digital triage tool that can be used rapidly and reliably, without the need for extensive memorization or training, by frontline health workers (including nurses and non-physician clinicians) to identify critically ill children (including those with sepsis). The digital platform consists of a mobile application integrating a pulse oximetry sensor attached to the device, with embedded smart algorithms that predict a critically ill state, or level of risk in a child presenting at the hospital. The platform also includes an interactive dashboard located in strategic locations (e.g., laboratory, consultation rooms), which connects to the mobile application through a secure local network and displays the triage data to provide real-time monitoring for the physicians who manage the patients.

Over the past 10 years, we have developed, implemented, and evaluated the core technology of the Digital Triaging Platform including vital sign measurement devices (PhoneOx [10] and RRate [11]) and the mobile application and dashboard [12–14]. We have already identified candidate predictor variables using a modified Delphi process [15], and developed a risk prediction model based on the need for admission using predictors collected in over 1000 children at a Kenyan hospital [16].

#### Methods/design

This protocol was developed with adherence to Standard Protocol Items: Recommendations for Interventional Trials (SPIRIT) guidelines.

## Objectives

#### Objective 1

To develop and clinically validate a digital triage tool and dashboard for improving hospital wait times to treatment administration in critically ill children, including those with sepsis.

This will involve:

- Collecting a pre-selected list of clinical variables (Additional file 1) from participants to develop a prediction model based on the need for hospital admission.
- b. Developing digital triage tool by implementing the derived prediction model along with ETAT triage guidelines (currently followed at study hospitals) into the Digital Triaging Platform.
- c. Evaluating the usability/feasibility of the digital trigger tool prior to implementation and routine use at the study hospitals.
- d. Determining effectiveness of the triage tool by comparing hospital wait times to treatment administration for children before and after implementation of the digital triage tool.

#### **Objective 2**

To validate the use of an automated Radio-Frequency Identification (RFID) method to track timeliness of interventions (see RFID system section more information). This will involve:

- a. Simultaneously having trained Timekeepers track patient wait times manually, and an RFID system track patient wait times automatically.
- b. Comparing time data obtained from the Timekeepers with time data obtained from the RFID system to evaluate accuracy of the RFID system.
- c. Achieving routine use of a clinically evaluated RFID system to automate tracking of patient wait times in the study hospitals.

#### Trial design

This is a pre-post intervention study concerning pediatric patients presenting to the study hospitals in seek of medical care for an acute illness. The study will take place over a period of 24 months. Participant recruitment will be initiated in April 2020 and continue for approximately 12 months. Statistical analysis, results presentation and dissemination will be conducted in the remaining months.

Study procedures can be divided into three phases: (I) pre-intervention (baseline), (II) interphase, (III) intervention (Table 1).

#### Phase I: pre-intervention (baseline)

This will be a period of baseline data collection at Mbagathi County Hospital, Jinja Regional Referral Hospital, and Kiambu County Referral Hospital. There will be no changes to healthcare delivery procedures in the hospitals. Triage in the pediatric outpatient department will continue as per usual by hospital nurses using ETAT guidelines [7]. Research nurses will consent participants and collect health data (see Additional file 1) in the triage waiting area, where patients are waiting to be seen by the hospital triage nurses. The control site, Kiambu County Referral Hospital will participate in Phase I for an elongated period of time (see Table 1) and will not participate in Phase II or Phase III.

#### Table 1 Study Schema

## Model derivation and technology development A risk

Phase II: interphase

prediction model will be derived using the data collected in Phase I and implemented in a Digital Triaging Platform, along with a digitized version of the ETAT+ guidelines. The Digital Triaging Platform, including vital sign measurement devices (PhoneOx [10] and RRate [11]) and the mobile application and clinical dashboard [12–14] has already been developed and evaluated. Once the digital triage tool has been developed, it will be evaluated in potential users using simulated patient scenarios and a 'Think Aloud' method.

Usability testing and training The digital triage tool will be evaluated for ease of interface navigation, functionality and basic workflow. A sample of 15 health workers in the study hospitals to represent the primary user groups will be selected for participation in the 60-min-long usability testing initiatives. Participants will be recruited through word of mouth as there is a very small cadre of potential participants. The objective of the training is to (1) ensure healthcare workers understand how to correctly collect and interpret patient information, and (2) to obtain feedback on the digitization of the tool. Training will use a framework that meets key international norms for testing digital tools, including, the think-aloud method and a questionnaire. Each training session will be conducted by a moderator and observer. During the evaluation, the observer will be seated next to the participant and will record user interaction with each interface, comments, errors, and duration of each task. Participants will be given 3-5 patient scenarios which will list hypothetical information to be entered into the app. This information will be designed to represent routine data collected during triage examination at the study hospitals. The moderator will provide the fictional charts to participants and instruct them throughout the tasks. During the simulated patient

Experimental Sites:	Phase I Baseline (3–5 months)	Phase II Interphase (1–3 months)	Phase III Intervention (5–6 months)	Post-Data Collection (9–14 months)			
1. Mbagathi County Hospital, Nairobi 2. Jinja Regional Referral Hospital, Jinja	Data collection of predictors and outcomes by study nurses.	Model derivation, technology development, usability testing.	Data collection continues as done in Phase I by study nurses. Routine use of digital triage tool by hospital nurses.	Analysis, results presentation and dissemination.			
Control Site:	Phase I (12 months)						
1. Kiambu County Hospital, Nairobi	Ongoing baseline data collection.						

scenarios, participants will be asked to think aloud, in order to assess their thought process as they used the app. Participants will be specifically instructed to comment on the layout of the app screen, the dialogue on each interface, the order of tasks, and any additional observations or opinions. After learning the basics of the digital platform, the participants will be read the think aloud instructions and asked to perform the list of tasks and answer questions. The observer will complete a checklist to ensure that all tasks were completed, questions will be asked to evaluate task comprehension, and notes will be taken about whether help was needed in completing each task. At the end of the training session, participants will complete a triage tool training questionnaire to provide an understanding of the practical benefits and drawbacks of incorporating the digital triage tool into a clinical context. The questionnaire will utilize open ended questions and comment responses. From this evaluation. Responses from the survey will be anonymous. The data generated from the training phase is fictitious and will not be linked to any individual subject. Transcriptions and Think Aloud observations will be analyzed using the Framework Method [17] to assess attitudes of health workers. Responses will be transcribed and coded using NVivo [18], for the identification, examination and interpretation of emerging themes and patterns. Results from the analysis, feedback from the questionnaires, and comments on the observer checklists will be used to generate a report with suggested improvements to be shared with the quality improvement implementation team prior to Phase III.

#### Phase III: intervention

Phase III will be an interventional period involving routine use of the digital triage tool by the **hospital triage nurses** at Mbagathi County Hospital in Nairobi, Kenya, and Jinja Regional Referral Hospital in Jinja, Uganda. The digital triage tool will not replace triage policies in place at the study hospitals, but rather it will strengthen existing systems by integrating ETAT guidelines and a data-driven risk prediction model into the application. As done in Phase I, **study nurses** will consent participants and collect health data in the triage waiting area while patients are waiting to be seen by **the hospital triage nurses** (who will be using the digital triage tool). Continued collection of predictor variables will allow comparison of participant characteristics in the preintervention cohort and the post-intervention cohort.

### Methods: participants, interventions, and outcomes

#### Study setting

This multi-site study will take place at one hospital in Uganda, and two hospitals in Kenya. In Uganda, the study will be conducted at Jinja Regional Referral Hospital in Jinja. Jinja, a city of approximately 90,000 people, is located in the Eastern region of Uganda. The Jinja Regional Referral Hospital pediatric ward admits approximately 5000 patients per year and the outpatient department sees approximately 100 patients per day. In Kenya, the study will be conducted at Mbagathi County Hospital and Kiambu County Referral Hospital, both located in Nairobi. A typical outpatient department (OPD) in the Kenyan study hospitals serves approximately 20, 000 children per year and is staffed by one or two nurses

who conduct triage and administer treatment, two or three clinicians who review patients and issue prescriptions, and one additional nurse who administers treatment and provides counselling to caregivers of children. The Kenyan hospitals admit approximately 2000 pediatric patients per year.

#### Study sites

- 1. Jinja Regional Referral Hospital, Jinja, Uganda (experimental site)
- 2. Mbagathi County Hospital, Nairobi, Kenya (experimental site)
- 3. Kiambu County Referral Hospital, Nairobi, Kenya (control site)

## Eligibility criteria Inclusion Criteria:

- 1. All pediatric outpatients seeking medical treatment of an acute illness. The lower age limit will include children aged from 0 days, and the upper age limit will be in accordance to respective hospitals' practice for pediatric admissions (this may be 12, 15 or 19 years).
- 2. Informed parental/guardian consent provided.
- 3. Assent from children older than 8 years (Uganda site) or 13 years (Kenya sites) in addition to parental/guardian consent provided.

#### **Exclusion Criteria:**

- 1. Patients presenting to the outpatient department for elective cases (e.g. elective surgery or change of dressing) or for clinical review appointment.
- 2. Informed consent or assent (when applicable) not provided.

#### Interventions

#### PRST (digital triage tool)

The PRST is a triage tool hosted on a digital platform that will enable frontline health workers in LMICs to identify critically ill children (i.e. severe infections, sepsis) early, so that life-saving treatment can be administered in a timely manner. The digital platform will consist of a mobile application hosted on an Android tablet integrating a pulse oximetry sensor attached to the tablet, with embedded smart algorithms that predict a critically ill state, or level of risk in a child presenting to the hospital. The platform will also include an interactive dashboard which will display the triage data to provide real-time monitoring for the clinicians who manage the patients. The dashboard will be implemented as a password protected website accessible by registered medical staff on any computer or tablet on the local network, allowing for easy and non-disruptive integration into health systems with existing electronic health records. ETAT+ criteria for triage will be incorporated as part of the digital platform (in addition to model identified from data obtained in Phase I).

#### **RFID** system

Timing tracking will be automated using customised RFID. RFID uses radio-frequency electromagnetic fields to identify the location of patients carrying special tags, with the help of readers located in key locations around the hospital, including the registration area, triage examination rooms, and treatment rooms. We intend to use Low Energy Bluetooth (BLE) tags that have a diameter of approximately 3 cm and weigh < 20 g. These tags will be inserted into a custom, washable arm, wrist or leg band. The tag could also be retained by the caregiver if the child was not willing to have the tag attached to them. When in close vicinity to a reader (for example, in the same room), the tag (location beacon) sends a message to a strategically located receiver to track the time at which the patient was in that precise location. The Bluetooth frequency is no different to that used by mobile phones and is not expected to interfere with other processes in the hospital. The RFID system will allow health workers to keep track of patients with ease and has the potential to increase organization in fast-paced, overburdened healthcare facilities.

### Outcomes

#### Primary outcomes

**For model development** Hospital admission (within 5 days of assessment) status determined from hospital records, and a follow up call 7 days post discharge. This will inform development of a clinical prediction model based on need for hospital admission.

For effectiveness evaluation of digital triage tool An increase of at least 20% in the proportion of critically ill children (emergency and priority cases) receiving an appropriate bundle of care within 60 min of arrival at the hospital. An appropriate bundle of care is defined as at

least one of antibiotics, intravenous fluids, or oxygen as appropriate for age and clinical syndrome as determined and administered by **hospital staff**.

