### 11. Outcomes

### **Primary Outcomes**

- 1. **Model Development:** Hospital admission (within 5 days of assessment) status determined from hospital records and information system, and a follow up call 7 days post discharge (to ascertain outcome). This will inform development of a clinical prediction model based on need for hospital admission.
- 2. Effectiveness Evaluation of Digital Triage Tool: Time to administration of an appropriate sepsis bundle of care, which includes at least one of antibiotics, intravenous

fluids, or oxygen as appropriate for age and clinical syndrome (treatment determined and administered by **hospital staff**). This will allow us to quantify the change from baseline in the proportion of children in each triage category (emergency, priority, queue) receiving treatment within 60 minutes of arrival at hospital.

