### **Power to Detect Difference Considerations**

We have estimated the proportion of children who currently receive a bundle of care within one hour in the pre-intervention group to be 27%, based on findings from previous studies [19] and confirmed in our feasibility trial of the application and dashboard in Uganda. We will need at least 750 children for each of the pre-intervention and post-intervention conditions, using an alpha of .05, at power of 80%, to detect a 20% decrease in the proportion of children who receive the bundle of care within one hour.

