#### **Outcomes Analysis**

We will compare the proportion of children at the two intervention sites receiving a completed bundle within 60 minutes to the historical and the contemporaneous control group (Marascuillo procedure). The median time to an appropriate bundle of care will be compared using a Mann–Whitney U test. The triage prioritization between the phases and the proportion of children who received and appropriate bundle of care within each triage categorization will be compared with Fisher's exact tests. Segmented regression analysis of the interrupted time series of the pre- and post- intervention periods will be used to assess immediate effects and effects over time, controlling for prior trends that may continue without our intervention. Quantile regression will be used to estimate the median differences. We will compare the estimated times at end of the intervention period with the expected counterfactual value, had the pre-intervention trend continued as if the intervention never occurred. We will compare the time to event (treatment bundle) using the Kaplan-Meier estimator with censure at 180 minutes. Secondary outcomes will be compared using generalized estimating equations.

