#### **Outcomes** analysis

We will be conducting our primary analysis using a difference in differences method. For our primary analysis, a logistic regression model for receipt of bundle of care within 1 h will be fit including: 1) phase of study (pre vs. post PRST) and 2) group (intervention versus control) as independent dummy variables and 3) their interaction. The interaction term corresponds to the difference in log-odds between groups in baseline vs intervention and it's exponent as the ratio of odds ratios. We will summarise this difference by estimating the marginal effect (risk difference) of phase in both the control and intervention groups. The difference of these marginal effects is the so-called 'difference in difference' for a binary outcome [24]. Confidence intervals will be based on the delta-method, or bootstrapping, where appropriate. A similar approach will be used for binary secondary outcomes (mortality, readmission), or quantile regression for median time to bundle of care, a non-parametric outcome.

Subgroup analyses specified a priori include Ugandan vs. Kenyan intervention site, young infant (under 2 months old) vs. children under 5 vs. older children, and presentation during day-shift hours versus night-shift hours (if applicable). We will also perform subgroup analyses on each triage category (emergency, priority, queue); patients from the pre-intervention phase will be retroactively categorized into these subgroups for this analysis. These subgroup analyses will be conducted with the inclusion of a three-way interaction between said variable, phase, and group. Statistical significance will be based on a likelihood ratio test comparing models with and without this term. This three-way interaction term would represent potential interactions between different subgroups and our difference in odds ratio obtained in our primary analysis, and results will again be presented on the risk difference scale based on marginal effects. This method of subgroup analysis sometimes termed a difference in difference in differences method.

Although none are expected, if there are any time varying confounders identified during the study that differ between intervention and control (health system or policy changes, natural events, changes in patient populations etc.) they will be included in above models as sensitivity analyses.

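### The published primary outcome is limited to emergency and priority children, but the primary model is not, and the sample size does not say which children it counts

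*Combined protocol and SAP*

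**What the plan says.** **Published protocol (June 2020).**

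- *Primary outcomes*: the effectiveness outcome is a rise of 20% or more "in the proportion of critically ill children (emergency and priority cases) receiving an appropriate bundle of care within 60 min".
- *Outcomes analysis*: for the primary analysis "a logistic regression model for receipt of bundle of care within 1 h will be fit" on phase, group and their interaction. No restriction by triage category is stated. Later in the same section: "We will also perform subgroup analyses on each triage category (emergency, priority, queue); patients from the pre-intervention phase will be retroactively categorized". These subgroups are tested with a three-way interaction.
- *Power to detect difference considerations*: 27% of children at baseline, a 20% relative increase, alpha 0.05, 80% power and 750 per group. No triage category is named.
- *Eligibility criteria* and *Sampling strategy*: acutely ill paediatric outpatients of any severity, selected by arrival time.

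**Protocol v5.0 (October 2020).**

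- *Section 11*: the primary effectiveness outcome is time to the bundle, which is then to be used to quantify "the change from baseline in the proportion of children in each triage category (emergency, priority, queue) receiving treatment within 60 minutes".
- *Section 17, Outcomes Analysis*: "We will compare the proportion of children at the two intervention sites receiving a completed bundle within 60 minutes" against the historical and contemporaneous controls. A Fisher's exact comparison within triage categories is also planned. Neither is called primary.
- *Section 13*: "We will need at least 750 children for each of the pre-intervention and post-intervention conditions", again without a triage category.

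Neither document gives the expected share of emergency and priority children.

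**The concern.** Queue can be a level of a subgroup factor only if queue children are in the analysed data. The published primary model therefore covers every enrolled outpatient, while the published primary outcome covers emergency and priority cases only. Both statements sit in one paper, so a revision between documents cannot explain the difference.

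The bundle is at least one of antibiotics, intravenous fluids or oxygen, where appropriate for the child. Many queue children may need none of these, so counting them in the denominator changes the quantity being estimated and probably shrinks it. If the point stays open, the population could be settled after the results are known. If the restriction is applied, the number analysed is only a fraction of the number enrolled, and the plan nowhere makes that conversion.

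**Working it through.** **1. The plan's own figure.** Inputs from the published sample size: p1 = 0.27, p2 = 0.27 × 1.2 = 0.324, alpha 0.05, power 80%, equal groups. With p̄ the mean of p1 and p2,

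n = [1.960·√(2p̄(1−p̄)) + 0.8416·√(p1(1−p1) + p2(1−p2))]² / (p2−p1)²

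Here p̄ = 0.297, so n = (1.960 × 0.6462 + 0.8416 × 0.6451)² / 0.054² = 3.274 / 0.002916 = 1,123 per group, two-sided.

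The stated 750 does not reproduce:

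- one-sided: 885;
- v5.0 power paragraph, a decrease to 21.6%: 990 two-sided, 779 one-sided;
- 20 percentage points: 91 (up) or 55 (down), two-sided.

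Two-sided power at 750 for 27% to 32.4% is 62.9%. The comparisons below therefore use 1,123 as the reference, not 750.

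**2. Assumptions not in the documents.** Emergency and priority share s, 20 to 60%. The 27% to 32.4% change applies to that group. Queue children have rate q in both phases, with q from 0 to 10% (central value 5%).

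**3. All children analysed.** The overall rate is s × p + (1−s) × q. With s = 0.4 and q = 0.05:

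- before: 0.4 × 0.27 + 0.6 × 0.05 = 0.138
- after: 0.4 × 0.324 + 0.6 × 0.05 = 0.1596
- n = (1.960 × 0.5033 + 0.8416 × 0.5031)² / 0.0216² = 1.9877 / 0.00046656 ≈ 4,260 per phase

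With q = 0 (10.8% to 12.96%) n is about 3,520. With q = 0.10 (16.8% to 18.96%) it is about 4,940.

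**4. Emergency and priority children only.** Enrolment needed is 1,123/s. If N are enrolled per phase, m = N·s are analysed, and two-sided power is Φ[(0.054·√m − 1.960 × 0.6462)/0.6451].

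| Share s | All-children n per phase (q = 5%) | Enrolment for 1,123 analysed | Power, N = 1000 | Power, N = 1,250 | Power, N = 4000 |
|---|---|---|---|---|---|
| 20% | about 12,050 | 5,615 | 22% (m = 200) | 26% (m = 250) | 66% (m = 800) |
| 40% | about 4,260 | 2,808 | 39% (m = 400) | 46% (m = 500) | 92% (m = 1,600) |
| 60% | about 2,380 | 1,872 | 53% (m = 600) | 63% (m = 750) | 98% (m = 2,400) |

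The 1000 is the Phase I minimum in both documents. The 1,250 adds v5.0's extra 250 per experimental site. The 4000 is the per-site target, used here as if it were a per-phase number. Neither document splits it by phase.

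All of this is for the two-group before-and-after comparison on which the plan is sized. The difference-in-differences contrast also carries the control group's variance, so it needs more in either population.

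**The case against.** Several points on the other side stand.

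- **A reader might infer that the sized and analysed populations differ.** On their face they do not: the published model and sample size are both unrestricted. The mismatch is between those two and the outcome definition. For the sample size, all children is only an inference from silence. The source cited for the 27% is, by its title, a neonatal sepsis study, so the rate may have been meant for sicker children.
- **A reader might infer that v5.0 sets three primary populations.** It does not. Its outcome is time to the bundle, and the per-category sentence describes a use of that outcome. It is also a later document, so its difference from the paper may be a revision.
- **A reader might infer that even 4000 enrolled would fall short of 750 emergency and priority children.** 4000 × 20% = 800 and 4000 × 60% = 2,400, both above 750. The larger sample was also chosen largely for model development, and v5.0 raises the Phase I minimum.
- **The dilution inputs are assumed.** The share, the queue rate and the absence of a queue effect appear nowhere in the plan. If the tool also speeds up bundles for queue children, dilution is smaller.
- **Part of the remedy is in place.** Category-specific results are planned, and study nurses collect the same predictors in both phases.

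None of this removes the conflict between the published outcome and the published primary model.

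**Conclusion.** The concern holds as a contradiction inside the published protocol, and v5.0 does not resolve it. Followed as written, the primary analysis answers a question about all enrolled outpatients, not the stated outcome in emergency and priority cases. The sample size cannot settle the matter, because it does not say to whom the 27% and the 750 apply.

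The cost depends on inputs the plan does not give. At an assumed 40% share with no queue effect, leaving queue children in raises the requirement to about 4,260 per phase, against 2,808 enrolled (1,123 analysed) with restriction on the same two-sided 5%, 80% power standard. With restriction, the Phase I minimum of 1000, if matched in Phase III, is inadequate across shares of 20 to 60%. A per-phase enrolment of 4000 is short of 80% power at a 20% share but ample at 40% and above. The documents therefore do not support a general statement that the trial is too small. They do support the statement that its primary population is not fixed.

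**What to change.** 1. In *Outcomes analysis* (published) and section 17 (v5.0), state that the primary model is fitted in emergency and priority children, as the published outcome defines them. Make all-children, queue and per-category results secondary, and reconcile v5.0 section 11 with this. If the sponsor prefers all children, the published outcome must be changed instead and the trial sized for the diluted effect.
2. State that one algorithm, applied to the study-nurse predictors, classifies children in both phases. The published plan pauses predictor collection for one month before and one month after implementation, so say how children from those months are classified or whether they are left out of the primary analysis.
3. In both sample-size sections, state the population to which the 27% applies and recompute the number per group for it. Do not simply relabel 750 as emergency and priority children, since it does not follow from the stated inputs.
4. Using the Phase I emergency and priority share, give the total enrolment this implies, or the power at the planned enrolment.

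The cost is wording, one recalculation, and probably a less favourable stated enrolment or power figure. No new data collection is needed.
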